6.1.1 Randomisation

Following written consent, participants are allocated at random to the control or Andoflex TLC Calamine Lite intervention group, using a randomised sequence from the freeware randomisation programme, see https://www.randomizer.org/. No stratified or block randomisation will be undertaken, apart randomisation per surgery type.

Sequential envelopes with each next randomisation allocation will be used to achieve concealment and these will be kept in the research department. The researcher or regular healthcare professional for the participant in question can e-mail ([contact]) or phone the R&D Dept ([name]) to determine which treatment the next participant has been allocated to.

6.2 Eligibility criteria

6.2.1 Inclusion criteria

- Patient who is listed for:
 - Knee arthroplasty (replacement) surgery, either partial or total knee replacement (single or double).
 - Unilateral high tibial osteotomy (HTO) or distal femoral osteotomy (DFO) or a double osteotomy (HTO and DFO) at one of participating NHS Trusts.
 - o In case of double procedure patients, one leg will be classed as the index leg and all outcomes measures will focus on said leg.
- Clinical indication, in the opinion of the treating surgeon, that dual-layer compression bandaging may be of benefit to the patient

- Adult patients aged > 18 years
- Mental capacity to give written informed consent

6.2.2 Exclusion criteria

- Under the age of 18 years
- Unable to fully understand the consent process and provide informed consent due to either language barriers or mental capacity
- Revision of previous knee replacement or osteotomy on the index leg.
- Limited life expectancy, i.e. undergoing palliative care
- Any condition that is associated with excessive bleeding, coagulation abnormalities or any other significant haematological condition (e.g. Factor V Leiden, haemophilia).
- Cardiovascular or vascular condition that in the opinion of the treating surgeon contraindicates the use of compression bandaging, including moderate to severe peripheral arterial disease, venous leg ulcer, high dose anti-coagulant medication
- Any skin or other condition that contraindicates the use of compression bandaging, including diabetic foot ulcer or peripheral neuropathy.
- Patients who are participating in another interventional research study involving an investigational product related to the knee procedure and its aftercare.
- The patient has concurrent (medical) conditions that in the opinion of the investigator may compromise patient safety or study objectives.
- Patient has practical or mobility issues which will prevent them from removing the bandage themselves

6.3 Early withdrawal of subjects

Patients have the right to withdraw from the trial at any time and without giving any reason. If a patient withdraws from the trial, any and all information gathered prior to the withdrawal will be excluded in the analysis, no further data collection will occur. If a patient does not attend a planned follow-up appointment then two more attempts will be made to contact the patient regarding the study. If still no contact can be made then the patient is deemed lost to follow-up and any collected study data will be retained.

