5.3 Consent and recruitment

Those eligible will be approached and provided with an information pack and consent form, which will be signed to indicate that informed consent has been given. Patients will be given ample time to

consider taking part, more than 24 hours if they wish. The study will be first mentioned at an orthopaedics out-patient clinic visit. The direct healthcare professional will first approach a patient about the study, and after verbal consent by the patient the healthcare professional themselves or a member of the research team can go through the informed consent process.

Patients are also allowed to consent to taking part when first approached as long as the study has been discussed with the patient and they have been given time to read the patient information leaflet and opportunity to ask any questions that they may have. Participants will receive no incentives and consent will be regarded as a process and not a one-off event. Participants are free to withdraw from the study at any time without the need to give any reasons for withdrawal. Their standard of care will not be affected by either declining to participate in the study or withdrawing during participation. Data collected up to the date of withdrawal will be retained for analysis.

Participants will be randomised to either the control bandage group (TaU) or the intervention group (Andoflex TLC Calamine Lite) any time up until the day of surgery.

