5.4 Follow-up

Patients are in the study for a period of 12 weeks. Thereafter, the patient will be followed up as they would be in normal clinical practice. Study visits are aligned to hospital/clinic visits where possible. Baseline data can be collected on the day of surgery (prior the actual operation), and 12 day and 12 week post-surgery data can be collected when the patient attends for standard follow-up in the orthopaedics out-patient department. The data at day 3, 5, day 12 and week 3 falls outside these dates. For all outcome measures, data can be collected over the phone, via e-mail or by mail (whichever is preferred by the patient – mail is by use of freepost, to avoid patients incurring any costs). The researcher can also send reminders to the participant regarding the completion of certain outcome data at the aforementioned follow-up time points.

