6. SUBJECTS

6.1 Anticipated number of research subjects

The sample size calculation does take into account a 20% patient attrition rate (withdrawal and loss to follow-up), since this involves a study with multiple time points for data collection up to 12 weeks. Patients will be recruited from the adult (age 18+) population routinely seen by the evaluating clinical staff members. The primary outcome measure is based on knee/leg (ie wound site) pain experienced 5-days post-surgery based on the VDS pain scale 'at rest'. The hypothetical difference in pain perception is 1.5 on a 10 cm scale which equates to a significant 'minimally clinically important difference' for pain (Kelly 2001; Lee et al 2003; Tashjian et al 2009). The values and differences observed in the ROBOT trial will be used for reference.

The non-parametric two-sided Mann-Whitney u-test is applied because the data is ordinal; 80% power and 5% significance is also applied. A priori power calculations using GPower 3.1 software, result in the following sample size summarized in Table 3.

Analysis will be performed on an intention-to-treat basis, although the number of days that a participant has worn a bandage will be recorded.

Data will be analysed as one cohort and also stratified by surgery type (knee replacement, osteotomy) in the resulting analysis.

Table 4, Sample size calculation

	Mean pain score at 5 days post-op	Standard Deviation
Arm A (hypothetical)	5.0	2

Arm B (hypothetical)	3.5	2			
	Power beta of 80%, Alpha p-value of 0.05, Effect size 0.75 Sample size required without any drop-out: 62 samples.				
	Sample size with 20% attrition rate included: 74				
	Total of 74 patients per surgery type:				
	- 37 Patients to receive non-compression bandaging				
	 37 Patient to receive Andoflex TLC Calamine Lite dual-layer compression bandaging 				
	Therefore total is: - 74 knee replacement cases - 74 osteotomy cases				
	Overall trial sample size: 148				

The CONSORT guidelines require a statement on the number of patients assessed for eligibility (Schulz, Altman & Moher 2010). The number of patients screened but who did not meet the inclusion criteria or who declined to participate will be recorded, as will any patients who are lost to follow-up (Appendix 3).

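### Sections 5.3 and 6.3 give opposite rules for data collected before a patient withdraws, and the 6.3 rule conflicts with the stated intention-to-treat analysis

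*Protocol*

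**What the plan says.** Three places in the protocol decide what happens to the data of a patient who leaves.

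- Section 5.3 (Consent and recruitment), on participants who withdraw: "Data collected up to the date of withdrawal will be retained for analysis".
- Section 6.3 (Early withdrawal of subjects), on patients who withdraw: "any and all information gathered prior to the withdrawal will be excluded in the analysis, no further data collection will occur". The same paragraph treats patients who cannot be contacted differently: after two further attempts, "the patient is deemed lost to follow-up and any collected study data will be retained".
- Section 6.1 (Anticipated number of research subjects): "Analysis will be performed on an intention-to-treat basis".

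The primary outcome is at-rest pain at day 5 (sections 5.5.1 and 6.1), but section 5.4 states: "Patients are in the study for a period of 12 weeks". A patient can therefore withdraw long after the primary outcome has been recorded.

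**The concern.** Both withdrawal rules are current operative text, and the protocol ranks neither above the other. An analyst who follows one breaks the other. A separate analysis plan could not cure this, because it would have to depart from one of the two sections.

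The 6.3 rule is the one out of line. It removes a randomised patient with an observed outcome because of something that happened after randomisation, and an intention-to-treat analysis is meant to prevent that. A patient who gave a valid day-5 score and withdrew in week 8 is in the primary analysis under 5.3 and out of it under 6.3.

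Two things are at stake. The first is bias. The bandages are visibly different in extent and wearing time (sections 3.1.1 and 3.1.2), pain is self-reported, and no blinding is described, so withdrawal could relate to both arm and pain. The second is the safety overview in section 8.3. Read literally, 6.3 would drop a patient who had a wound infection, thrombosis or readmission and then withdrew.

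**Working it through.** **Step 1. Where the two rules give different answers.**

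| Patient | Section 5.3 | Section 6.3 | Primary endpoint affected? |
|---|---|---|---|
| Withdraws before giving a day-5 score | Baseline, any day-3 data and safety events to date are analysed | All of these excluded | No: there is no day-5 score under either rule |
| Withdraws after giving a day-5 score, up to week 12 | Day-5 score analysed | Day-5 score excluded | Yes |
| Lost to follow-up | Not addressed | Data retained | No |

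So the primary comparison is exposed only through active withdrawal in the roughly 11 weeks after the day-5 score. Baseline, day-3 and safety data are exposed through withdrawal at any time.

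**Step 2. The plan's own sample size, and whether the contradiction changes it.**

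Inputs (section 6.1 and Table 4): difference 1.5 cm, SD 2 cm, two-sided 5% significance, 80% power, Mann-Whitney test.

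- Effect size: 1.5 / 2 = 0.75, as stated.
- Two-sample t-test: 28.9 per arm.
- Mann-Whitney efficiency under normality, 3/π: 28.9 / (3/π) = 30.3, so 31 per arm and 62 per surgery type. This reproduces the stated 62.
- Attrition: 62 × 1.2 = 74.4, the stated 74. (Dividing by 0.8 would give 77.5, rounded up to 78; that is a separate matter.)

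No stated figure depends on which withdrawal rule is used. Mann-Whitney power at an effect size of 0.75 is as follows:

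| Patients removed | Left of 74 | Power |
|---|---|---|
| none | 74 | 87.5% |
| 10% | 66.6 | 83.7% |
| 20% | 59.2 | 79.1% |

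For the pooled 148 with 20% removed, power is 97.7%. Lost precision is therefore a minor part of the problem.

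**Step 3. Size of a possible bias (assumed values).**

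Suppose a fraction f of one arm is excluded, and their mean day-5 pain is D cm above that of the patients who remain, whose mean is m.

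- Full arm mean: (1 − f)m + f(m + D) = m + fD.
- Mean after exclusion: m.
- Shift: −fD.

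The protocol gives neither f nor D. Over an assumed range:

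| f | D = 1 cm | D = 2 cm | D = 3 cm |
|---|---|---|---|
| 5% | 0.05 | 0.10 | 0.15 |
| 10% | 0.10 | 0.20 | 0.30 |
| 20% | 0.20 | 0.40 | 0.60 |

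Against the 1.5 cm target, the ends of the range are 0.05 / 1.5 = 3% and 0.6 / 1.5 = 40%.

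The f = 20% row is an extreme upper bound. It needs the whole attrition allowance in one arm to be active withdrawal after day 5. The allowance also covers loss to follow-up, whose data 6.3 keeps, and withdrawal before day 5, where there is no score to lose. If both arms lose similar patients, the shifts largely cancel. The primary test is Mann-Whitney, so a shift in means only approximates the effect on it.

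The only related data in the protocol are in Table 1, an earlier osteotomy trial of a different compression bandage. There, 18 per arm had day-5 scores, and 16 and 17 had 6-week scores: losses of 2/18 = 11% and 1/18 = 6%. Reasons are not given, so these are not withdrawal rates.

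**The case against.** The best counter-argument is that the mechanism for bias is weak in the period that matters. Discomfort from five days of compression would act mostly before or around the day-5 score, and a patient who leaves before giving that score contributes none under either rule. Discomfort also need not lead to withdrawal: section 3.1.2 lets patients remove the bandage early or have it reapplied, and section 6.1 records days worn. This stands. Allocation-related withdrawal after day 5 is possible, but nothing in the protocol shows it.

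A second argument is that 6.3 contains a drafting slip, and that the author meant to include the data. That would fit 5.3, the intention-to-treat statement and the rule for patients lost to follow-up. It is plausible, but the current text says excluded, so it still has to be corrected.

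A third is that treating active withdrawal differently from non-response is not in itself an error, since a patient who decides to leave may have been promised something about their data. That is fair, and it is why the leaflet and consent form need checking. It does not reconcile 5.3 with 6.3, because both concern patients who withdraw.

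A reader might also infer more than the documents support:

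- That a fifth of patients would drop out of the primary analysis. The 20% is not a rate of active withdrawal after day 5; no such rate is given.
- That the result will be biased by a known amount. The values of f and D are assumed.
- That patient records are destroyed. The text speaks only of exclusion from the analysis.
- That the protocol declares an open-label design. This is inferred from the bandages and the absence of any described blinding.

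**Conclusion.** The contradiction is real and rests on the text alone: 5.3 and 6.3 cannot both be followed, and 6.3 as written conflicts with intention-to-treat. It leaves undefined whether a patient who withdraws after day 5 is in the primary analysis, and whether any withdrawn patient counts in the baseline, day-3 and safety summaries.

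The effect on the primary result is possible rather than shown. It requires active withdrawal after the day-5 score that is related to both arm and pain. Under the assumed values above, the shift in one arm's mean is 0.05 to 0.6 cm against a 1.5 cm target, with the upper end extreme and the net effect smaller if both arms lose similar patients. The case for correction does not depend on that figure: the rule is wrong as written and very cheap to put right.

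**What to change.** Replace the exclusion sentence in section 6.3 with the 5.3 rule. New data collection stops at withdrawal, and all data collected up to that date are retained and analysed in the arm as randomised. State explicitly that any patient with a day-5 score stays in the primary analysis whatever happens later, and that safety events recorded before withdrawal stay in the section 8.3 overview.

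Confirm that the patient information leaflet and consent form, which are not available here, tell participants the same. Make the change before any comparison by arm, including the analysis planned in section 9 at 50% of the sample.

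The cost is one replaced sentence in the protocol and a consistency check of two participant documents. Sample size and test do not change.

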3.1.2 Andoflex TLC Calamine Lite compression bandaging (intervention) arm

As with standard bandaging, the Andoflex TLC Calamine Lite compression bandage will be applied over the routine surgical wound dressing. A foam inner bandage (Andoflex TLC Calamine Lite 2, Milliken Healthcare) is applied from the toe to the groin on the affected leg with minimal overlap. The second layer, which is the actual compression bandage (Andoflex TLC Calamine Lite 2, Milliken Healthcare) is applied at full stretch and with a 50% overlap of bandage to ensure adequate

compression in the application. The mode of action of this two layer compressive bandage kit is of particular practical use, since it is tolerable for patients overnight due to its low resting pressure. Furthermore, it produces high pressure compression with movement to stimulate the calf muscle pump. The bandage is applied from the toes upwards. The application of bandage from thigh to groin requires removal of the tourniquet first and so the leg is kept elevated until the bandaging is complete. There is a training video available on correct application of the bandages: https://www.youtube.com/watch?v=pal0pY_cTRc (Andoflex is known as Coflex in some other countries such as the USA).

The compression bandage has been shown to effect compression for up to a week. To balance compression and comfort, patients are asked to continue wearing the bandage for 5 consecutive days after surgery. The bandages can be removed sooner if the patients find them very uncomfortable (which will be classed as an adverse event) or in the event of any other adverse events that would require their removal – this will be recorded on the Case Report Form and in medical notes. If requested by the patient, they are allowed to return to a hospital clinic to have the Andoflex TLC Calamine Lite bandaging reapplied if for any reason the first set needed to be taken off. To maintain consistency, clinical healthcare professionals who apply a new Andoflex TLC Calamine Lite bandage need to sign a declaration that they have watched the training video and are comfortable complying with the instructions. Full product information on the Andoflex TLC Calamine 2-layer compression system can be found on the Andover Healthcare Inc website https://andoverhealthcare.com/product/coflex-tlc-calamine/

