8.3 Secondary outcome statistics

The average baseline demographics for participants in each group will be compared to ascertain that randomisation has indeed led to comparable distribution of participants:

Sex, age, height, weight, BMI, length of stay, type of anaesthetic for surgery and type of analgesics post-surgery.

To compare outcomes between the two groups (standard vs Andoflex TLC Calamine Lite bandaging), student t-test, Mann-Whitney U-test or Chi-squared test will be applied as applicable, depending on type and distribution of data .

Cox proportional hazards regression analysis will be conducted to investigate the role of bandaging and other covariates (as mentioned above) in post-surgery related pain and knee function.

The statistics apply to:

Up to 12 weeks prior to surgery, and 12 weeks post-surgery, knee function and quality of life measurements: Knee and Osteoarthritis Outcome Score (KOOS), and range of movement of the affected limb (goniometer)

Descriptive safety overview at 30 days and 12 weeks post-surgery:

- Readmitted to theatre and/or hospital
- Infection of wound site
- Diagnosed with pulmonary embolism or deep vein thrombosis
- All monitored remotely by review of patients' hospital notes.

Patient satisfaction survey at 12 days post-surgery – any difference in outcome will be determined with Mann-Whitney U-test

For all outcome measures and statistics, both whole cohort and surgery-specific stratification analysis will be conducted.

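### Section 6.3 stops all data collection at withdrawal, although the 30-day and 12-week safety outcomes come from hospital notes and need no patient contact

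*Protocol*

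**What the plan says.** Section 6.3 has one rule for patients who withdraw. For data after that point it says "no further data collection will occur". It makes no exception for safety and does not distinguish a patient who is tired of questionnaires from one who refuses any further use of their records. Patients who miss an appointment and do not answer two further attempts are handled separately: "If still no contact can be made then the patient is deemed lost to follow-up", and what was collected is kept.

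Section 8.3 plans a "Descriptive safety overview at 30 days and 12 weeks post-surgery", covering return to theatre or readmission, wound infection, and pulmonary embolism or deep vein thrombosis. On the source of these outcomes it says: "All monitored remotely by review of patients' hospital notes".

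Section 3.1.2 deals with early removal of the compression bandage: "The bandages can be removed sooner if the patients find them very uncomfortable (which will be classed as an adverse event"). It does not call this withdrawal. Section 6.1 states an intention-to-treat analysis, with days of wear recorded, and the Introduction (section 2) names safety as an aim alongside effectiveness.

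**The concern.** The safety outcomes are among the few in this trial that do not depend on the patient returning anything. A researcher can read them from the notes for every operated patient who permits it. The stop rule in 6.3 nevertheless ends that reading for everyone who withdraws, whatever the reason. A patient who formally leaves in the first week and has a DVT diagnosed the week after would not appear in the safety overview, although the event is in the notes.

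The result is under-ascertainment of harms in a comparison where counts will be small and one or two events can alter the picture. It also sits badly with the intention-to-treat principle and the stated safety aim. A statistical analysis plan cannot repair it, because data that were never collected cannot be analysed.

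**Working it through.** **Reading the rules together**

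- Section 6.3: after withdrawal, nothing more is collected, without exception.
- Section 8.3: safety outcomes at 30 days and 12 weeks come from the notes, without patient contact.
- Section 5.3: "Data collected up to the date of withdrawal will be retained for analysis". This concerns data before withdrawal and provides for nothing afterwards.
- Section 7.3 (adverse event reporting): no provision for patients who have left.

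No section of the protocol exempts the notes review from the stop rule.

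**Scale**

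The protocol gives no figure for missed safety events, so there is none to reproduce. What follows is illustrative and covers DVT only, because the protocol quotes no rate for infection, readmission or PE.

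Inputs from the protocol:
- Overall sample 148 (section 6.1), so 148 / 2 = 74 per arm over both surgery types.
- DVT in 2 of 47 high tibial osteotomy patients (section 2): 2 / 47 = 4.26%.
- Attrition allowance of 20% (section 6.1), covering withdrawal and loss to follow-up together. As planned, 20% is therefore an upper bound for withdrawal alone.

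Assumptions, not in the protocol:
- A fraction w of each arm withdraws before any event, with w from 5% to 20%.
- Those who stay have the quoted DVT rate. Those who withdraw have k times that rate, with k from 1 to 3.

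Formulas per arm:
- missed = 74 × w × k × 2/47
- captured = 74 × (1 − w) × 2/47
- share missed = missed / (missed + captured)

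| w | k | captured | missed | share missed |
|---|---|---|---|---|
| 5% | 1 | 2.99 | 0.16 | 5% |
| 5% | 3 | 2.99 | 0.47 | 14% |
| 10% | 1 | 2.83 | 0.31 | 10% |
| 10% | 3 | 2.83 | 0.94 | 25% |
| 20% | 1 | 2.52 | 0.63 | 20% |
| 20% | 3 | 2.52 | 1.89 | 43% |

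Lowest corner: 74 × 0.05 × 1 × 0.0426 = 0.16. Highest corner: 74 × 0.20 × 3 × 0.0426 = 1.89. The range is about 0.2 to 1.9 missed DVTs per arm, against about 3.1 to 4.4 expected.

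**The case against.** Ending collection at withdrawal is a cautious consent position, and some sponsors choose it deliberately. The safety overview is descriptive, and the powered day-5 pain endpoint is not what this point addresses. The consent form is not among the documents reviewed and may already permit continued notes review. All of this stands. It limits the weight of the point but does not remove the mismatch between 6.3 and 8.3.

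Four stronger readings are tempting, and the documents do not support them.

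- *Patients who take the bandage off early are lost to the safety count.* Section 3.1.2 allows early removal, records it as an adverse event when discomfort is the reason, and permits reapplication. Under intention to treat these patients stay in the trial.
- *Patients who cannot be reached are lost to the safety count.* The stop rule is written for withdrawal only. For patients lost to follow-up, 6.3 keeps the collected data and says nothing against reading the notes.
- *Harms are under-counted mainly in the compression arm.* This is plausible: that bandage runs from toe to groin for 5 days, the control covers the knee region for about 48 hours, and section 7.1 acknowledges skin reactions, discomfort and effects on blood flow. It remains an inference. The only retention data in the protocol (Table 1, a small trial of a different compression product) show 18 per arm with no reduction noted at days 5 and 12, and 16 in standard care against 17 with compression at 6 weeks. The numbers are too small to settle the question, but they show no greater loss under compression.
- *About 30 patients (0.20 × 148 = 29.6) fall under the stop rule.* The 20% includes loss to follow-up, and some events would come before withdrawal.

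**Conclusion.** The point holds in a limited form. As written, readmission, wound infection and DVT or PE after a formal withdrawal go uncounted, although they could be read from the notes without contact. On the assumptions shown, about 0.2 to 1.9 DVTs per arm would be missed. The upper end needs withdrawal to use up the whole attrition allowance before any event and a threefold risk that has no source in the protocol. The DVT rate rests on two events in osteotomy patients, while half of this trial is knee replacement. Whether the loss would differ between arms cannot be determined from the documents.

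A neighbouring conflict bears on the size. For data before withdrawal, 6.3 says "any and all information gathered prior to the withdrawal will be excluded in the analysis", whereas 5.3 retains them. If 6.3 governs, safety events recorded before withdrawal are dropped as well, and the loss is wider than calculated here. That conflict needs reconciling in its own right.

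This is an inexpensive improvement to a secondary, descriptive part of the trial and does not threaten the primary analysis.

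**What to change.** In section 6.3, separate two kinds of withdrawal:

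1. The patient leaves questionnaires and visits. The notes review already planned for 30 days and 12 weeks continues.
2. The patient withdraws consent to any further use of data, including the notes. All collection stops.

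Check that the consent form permits notes review after the first kind, and add a line if it does not. Add one sentence stating that early bandage removal alone is not withdrawal, and one stating that the notes review continues for patients lost to follow-up. In section 8.3, state that the safety overview covers all randomised and operated patients whose data use is permitted, and give by arm the number for whom it is not.

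The cost is protocol and possibly consent wording, with an ethics amendment. The review itself is already planned for the other patients, so the added work is small. Some patients may still refuse, and their events will remain unknown.

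### Section 6.3 makes a patient lost to follow-up after one missed appointment and two failed contacts, and does not provide for approaching them at later time points

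*Protocol*

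**What the plan says.** Section 6.3 of the protocol handles two situations in one paragraph.

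- **Withdrawal.** For a patient who withdraws, "any and all information gathered prior to the withdrawal will be excluded in the analysis, no further data collection will occur".
- **Non-attendance.** "If a patient does not attend a planned follow-up appointment then two more attempts will be made to contact the patient regarding the study". The consequence follows: "If still no contact can be made then the patient is deemed lost to follow-up and any collected study data will be retained".

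Four other places bear on this:

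- Section 6.1 allows 20% for attrition and names withdrawal and loss to follow-up as its two components. It also says that patients lost to follow-up will be recorded for the CONSORT account.
- Section 5.4 says that "12 day and 12 week post-surgery data can be collected when the patient attends for standard follow-up", and also that "For all outcome measures, data can be collected over the phone, via e-mail or by mail". Reminders are allowed.
- Table 3 in section 5.5.2 has five post-surgery time points: days 3, 5 and 12, and weeks 6 and 12. Pain scales and the McGill questionnaire run to week 6, range of motion is at week 6, and KOOS is at weeks 6 and 12. The protocol summary also lists range of motion at week 12.
- Section 8.3 takes readmission, wound infection and thromboembolic events at 30 days and 12 weeks from records: "All monitored remotely by review of patients' hospital notes".

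**The concern.** A patient who cannot be reached around one time point has not withdrawn consent and may well answer at the next. Section 6.3 has no category for a missed time point. It goes straight from one missed appointment, with two failed attempts, to a status for the whole patient that the sample-size section treats as attrition. Staff who follow it as written could reasonably stop approaching the patient.

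The outcomes at stake are mainly the late secondary ones: week-6 pain and range of motion, and KOOS at weeks 6 and 12. Patients who are hard to reach soon after knee surgery may differ in pain or recovery from those who are easy to reach, so the missing scores could be informative. Section 6.1 commits to an intention-to-treat analysis, and continued collection serves that better than an early end to contact.

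**Working it through.** **1. What the text settles and what it leaves open**

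| Question | Protocol text |
|---|---|
| Trigger | One unattended follow-up appointment, then two failed attempts (6.3) |
| Unit of the status | The patient (6.3); counted as attrition (6.1) |
| Data already held | Retained (6.3) |
| Later collection stopped? | Stated only for withdrawal; silent for loss to follow-up (6.3) |
| Later collection attempted? | Not stated (6.3) |
| Later collection feasible? | Yes, by phone, e-mail or mail (5.4), although range of motion uses a goniometer (8.3) and in practice probably needs attendance |
| Notes-based safety review | Not stopped by 6.3; needs no contact (8.3) |

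**2. Which time points can trigger the rule**

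The trigger word is appointment. Section 5.4 links day 12 and week 12 to clinic attendance and puts days 3 and 5 outside it (day 12 appears on both sides).

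- *Narrow reading:* only day 12 and week 12 count. Both come after day 5, so the primary endpoint is untouched. A miss at week 12 costs only week 12, under any rule. The rule therefore matters only for a miss at day 12.
- *Broad reading:* every Table 3 time point counts. A missed day-3 contact could then cost the day-5 score.

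The narrow reading is the more natural one.

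**3. The plan's own figure**

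A two-sided Mann-Whitney test with effect size 0.75, alpha 0.05 and relative efficiency 3/π needs 31 per arm for 80% power (achieved 0.810), so 62 in all. Then 62 × 1.2 = 74.4, which matches the stated 74 per surgery type. The calculation is for day-5 pain at rest. The 20% allowance therefore protects the day-5 comparison, not week 6 or week 12.

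**4. Illustration of size, by assumption only**

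Let m be the probability that a patient meets the full trigger at a time point. The protocol gives no value; 3%, 5% and 8% are assumed.

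Narrow reading, with later non-response also m and independent of the first: missing at a later time point is m if patients stay in the schedule and 1 − (1 − m)² if they do not. The excess is m(1 − m).

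| m | Excess missing at weeks 6 and 12 | Of 148 patients |
|---|---|---|
| 3% | 0.03 × 0.97 = 2.9% | 4.3 |
| 5% | 0.05 × 0.95 = 4.75% | 7.0 |
| 8% | 0.08 × 0.92 = 7.4% | 10.9 |

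If the patients missed at day 12 would be unreachable later in any case, the excess is zero.

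Broad reading, independent contacts, cumulative loss 1 − (1 − m)^k:

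| m | By day 5 (k = 2) | By week 12 (k = 5) |
|---|---|---|
| 3% | 5.9% | 14.1% |
| 5% | 9.8% | 22.6% |
| 8% | 15.4% | 34.1% |

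Reaching 20% needs m = 1 − 0.8^(1/5) = 4.4% over five contacts, but m = 1 − 0.8^(1/2) = 10.6% over the two contacts up to day 5.

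**The case against.** The strongest reply is that permanence is not written down. The sentence that ends data collection applies to withdrawal only. For loss to follow-up the text keeps what has been collected and says nothing about the future, so a patient who reappears is not barred. Table 3 even allows the satisfaction questionnaire at week 6 if it was not returned by day 12, so the protocol does expect some late answers. The rule is a common operational definition, and contact details are often left to working instructions. This stands in part: the text does not forbid later contact. It does not provide for it either, and the Table 3 fallback covers one unreturned form, not a patient who has already been given the status.

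A reader might infer three stronger points. The protocol does not support them:

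- *That one early miss removes all later outcomes for good.* Section 6.3 does not say so, and the safety outcomes come from hospital notes without contact.
- *That the rule endangers the primary endpoint.* This needs the broad reading of appointment. Even then, about half of the loss by day 5 is day-5 non-response itself, which no rewording would recover.
- *That the rule can by itself exceed the 20% allowance.* This needs an assumed rate above 4.4% at each of five contacts, independence between contacts, and the broad reading. Hard-to-reach patients tend to be the same people each time; with full clustering, 5% stays 5%. The allowance also already includes loss to follow-up and was set for day 5, where the assumed rates of 3% to 8% stay below 20%.

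**Conclusion.** The point holds as a cheap improvement to a stated operational rule, not as an error in the design or the sample size. Section 6.3 turns one missed appointment and two failed contacts into a status for the whole patient and does not say that later time points are still attempted. On the ordinary meaning of that status, patients who miss day 12 risk losing week-6 pain and range of motion and week-6 and week-12 KOOS, some of it avoidably and possibly informatively.

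The size is unknown. The narrow-reading illustration gives zero to about 7 percentage points of extra missing data at weeks 6 and 12, and it rests on assumed rates of 3% to 8%. No conclusion about the 20% allowance follows. The conclusion also assumes that the flowcharts in Appendices 2 and 3, which could not be read in the text available, do not provide for further approaches.

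**What to change.** Reword section 6.3 as follows:

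- After two failed attempts, that time point is recorded as missed.
- A patient who has not withdrawn is approached at each later time point in Table 3, by any route that section 5.4 allows.
- Loss to follow-up is assigned only if contact has not been regained by the close of the week-12 window.
- The 30-day and 12-week review of hospital notes continues for these patients.
- The text says whether appointment means the clinic visits only or every Table 3 time point.

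The cost is a few sentences of protocol wording, with whatever approval such a change needs, and a few more calls, e-mails or letters by existing staff. The sample size, outcomes and tests do not change.
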